8 ASSESSMENT OF SAFETY

8.1 SPECIFICATION OF SAFETY PARAMETERS

All HD carries a risk of low BP, heart rhythm abnormality, electrolyte abnormality, and bleeding. Patients are exposed to these risks each time they undergo dialysis. Participation in this study will not increase these baseline risks. There are no known risks associated with UF profiling. All study monitoring is low risk and part of routine dialysis care. The study involves one non-standard blood draw (Troponin T) which will be taken from the vascular access and not require a separate “stick” and one non-standard monitoring test (TTE) which is non-invasive and free of discomfort or complications.

8.1.1 DEFINITION OF ADVERSE EVENTS (AE)

An adverse event (AE) is any untoward medical occurrence (e.g., an abnormal laboratory finding, symptom, or disease temporally associated with the use of the experimental treatment) in a patient or clinical investigation subject administered an experimental treatment and which does not necessarily have a causal relationship with this treatment. An AE can therefore be any unfavorable and unintended sign (including an abnormal vital sign finding) or symptom temporally associated with the use of the experimental treatment, whether or not related to the experimental treatment. Each AE will be graded on a mild-moderate-severe scale. Hospitalization for elective surgery or routine clinical procedures that are not the result of an AE (e.g., surgical insertion of central line) need not be considered AEs and should not be recorded as an AE.

A suspected adverse reaction (SAR) is any AE for which there is a *reasonable possibility* that the experimental treatment is the cause. *Reasonable possibility* means that there is evidence to suggest a causal relationship between the experimental treatment and the AE. A suspected adverse reaction implies a lesser degree of certainty about causality than adverse reaction, which means any adverse event caused by an experimental treatment. Each SAR will be graded on a mild-moderate-severe scale.

Causality assessment to an experimental treatment is a medical judgment made in consideration of the following factors: temporal relationship of the AE to the experimental treatment exposure, known mechanism of action or side effect profile of study treatment, other recent or concomitant drug or treatment exposures, normal clinical course of the condition under investigation, and any other underlying or concurrent medical conditions. Other factors to consider in considering drug as the cause of the AE:

- One or more occurrences of an event not commonly associated with experimental treatment exposure, but otherwise uncommon in the population (e.g. severe symptomatic hypotension); often more than one occurrence from one or multiple studies would be needed before the study oversight physician could determine that there is *reasonable possibility* that the experimental treatment caused the event.
- An aggregate analysis of specific events observed in a clinical trial that indicates the events occur more frequently in the experimental treatment group than in the control group.

8.1.2 DEFINITION OF SERIOUS ADVERSE EVENTS (SAE)

An AE is considered serious (SAE) if, in the view of the study oversight physician, it results in any of the following outcomes:

- Death
- Is life-threatening (places the subject at immediate risk of death from the event as it occurred)
- Requires inpatient hospitalization (>24 hours) or prolongation of existing hospitalization
- Results in a persistent or significant incapacity or substantial disruption of the ability to conduct normal life functions

- Important medical events that may not result in death, be life-threatening, or require hospitalization may be considered a serious adverse experimental treatment experience when, based upon appropriate medical judgment, they may jeopardize the patient or subject and may require medical or surgical intervention to prevent one of the outcomes listed in the definition.

*Hospitalization for anticipated or protocol specified procedures such as administration of chemotherapy, central line insertion, metastasis interventional therapy, resection of primary tumor, or elective surgery, will not be considered serious adverse events.

8.1.3 DEFINITION OF UNANTICIPATED PROBLEMS (UP)

An AE or SAE is considered unexpected if the specificity or severity of it is not consistent with the applicable experimental treatment information (e.g., dialysis machine approved product brochure).

8.2 CLASSIFICATION OF AN ADVERSE EVENT

8.2.1 SEVERITY OF EVENT

Each AE will be graded on a mild-moderate-severe scale by the monitor as described above.

8.2.2 RELATIONSHIP TO STUDY EXPERIMENTAL TREATMENT

An AE or SAE will be considered potentially related to the study experimental treatment if it occurs during an HD treatment in which the experimental treatment (UF profiling) is being administered.

8.2.3 EXPECTEDNESS

There are no known expected AE or SAEs associated with the study experimental treatment (UF profiling). An AE will be considered unexpected if the nature, severity or frequency of the event is not consistent with the risk information previously described for the study agent.

8.3 TIME PERIOD AND FREQUENCY FOR EVENT ASSESSMENT AND FOLLOW-UP

The occurrence of an AE or SAE may come to the attention of study personnel during study visits or upon review by a study monitor. All AEs not meeting the criteria for SAEs will be captured on the appropriate case report form. Information to be collected includes event description, time of onset, clinician's assessment of severity, relationship to the study intervention, and time of resolution/ stabilization of the event. All AEs occurring while on study must be documented appropriately regardless of relationship. All AEs will be followed to adequate resolution.

Any medical condition that is present at the time that the participant is screened will be considered as baseline and not reported as an AE. However, if the study participant's condition deteriorates at any time during the study, it will be recorded as an AE. Unanticipated problems will be recorded in the data collection system throughout the study.

Changes in the severity of an AE will be documented to allow an assessment of the duration of the event at each level of severity to be performed. AEs characterized as intermittent require documentation of onset and duration of each episode.

The PI will record all reportable events with start dates occurring any time after informed consent is obtained until 7 (for non-serious AEs) or 30 days (for SAEs) after the last day of study participation.

8.4 REPORTING PROCEDURES

8.4.1 ADVERSE EVENT REPORTING

Events meeting the criteria for an AE will be documented within 24 hours of occurrence. A summary of AEs, including evaluation of the AEs by the monitor will be submitted to the IRB at the time of the progress report.

8.4.2 SERIOUS ADVERSE EVENT REPORTING

Events meeting the criteria for an SAE will be documented within 24 hours of occurrence. The IRB will be notified of all SAEs that qualify as an unanticipated problem as per the UNC IRB policies within 7 days of the investigator being notified of the event.

8.4.3 UNANTICIPATED PROBLEM REPORTING

Events meeting the criteria for an unanticipated problem will be documented within 24 hours of occurrence.

8.4.4 EVENTS OF SPECIAL INTEREST

N/A

8.4.5 REPORTING OF PREGNANCY

Pregnancies (including a positive pregnancy test regardless of age or disease state) of a female subject occurring while the subject is enrolled will result in study cessation for the pregnant subject. The female subject will be referred to an obstetrician-gynecologist. Pregnant dialysis patients require more intensive dialysis therapy and are not appropriate for ongoing study participation. The Investigator will follow the female subject until completion of the pregnancy, and must document the outcome of the pregnancy (either normal or abnormal outcome). If the outcome of the pregnancy was abnormal (e.g., spontaneous or therapeutic abortion), the Investigator should report the abnormal outcome as an AE. If the abnormal outcome meets any of the serious criteria, it must be reported as an SAE.

8.5 STUDY HALTING RULES

If there is an SAE suspected to be related to the study intervention, UF profiling, the study will be put on hold and re-evaluated as this would not be an expected event.

8.6 SAFETY OVERSIGHT

The PI will provide continuous, close monitoring of the study. Trained dialysis nurses and technicians will administer the HD treatments per routine care and will have 24-hour telephone and pager access to the PI. A licensed dialysis physician will also be immediately available to the HD units during study HD treatments. Participating patients will be given the PI's direct contact information. If there is concern for an AE or SAE, an attending nephrologist (other than the PI who will be blinded to study treatment arm) will assess and record any AE or SAE in detail including the time of onset, description, severity, time course, duration, and outcome, relationship of the AE/SAE to study arm, and any action(s) taken. Two additional attending nephrologists will review study-associated morbidities no more than two days after they occur in order to determine whether further safety guards should be instituted and whether the benefit of the study continues to outweigh potential risks. The PI will report all adverse events to the IRB and funding institute and center on the day of occurrence. The PI will discuss all morbidities with project co-investigators. The PI will personally review all study results and notify

subjects of any abnormal results, including those present at baseline unrelated to the treatment to ensure subjects are able to seek appropriate medical care.

9 CLINICAL MONITORING

Clinical site monitoring is conducted to ensure that the rights and well-being of human subjects are protected, that the reported trial data are accurate, complete, and verifiable, and that the conduct of the trial is in compliance with the currently approved protocol/ amendment(s) and with GCP. The PI and research Study Coordinator will conduct on-site monitoring (at least once per study phase) and centralized monitoring (every study treatment) for all study participants at all study sites to verify protocol adherence/ study conduct, data collection, and safety.

10 STATISTICAL CONSIDERATIONS

10.1 STATISTICAL AND ANALYTICAL PLANS

This is an investigator-initiated 4-period cross-over trial. Statistical and analytical plans were developed in consultation with statistical experts. See below for details.

10.2 STATISTICAL HYPOTHESES

We hypothesize that patients will have comparatively less hypotension, troponin change and left ventricular global longitudinal strain change with UF profiling vs. conventional HD.

10.3 ANALYSIS DATASETS

Analytical datasets will be compiled from collected clinical data. Datasets will include an intention-to-treat analysis dataset and a modified intention-to-treat analysis dataset. Data analysis will be performed with STATA 12.2MP. Datasets will be de-identified and maintained on a secure UNC Department of Medicine Server that is accessed via a password-protected UNC computer with anti-virus and UNC firewall protection.

10.4 DESCRIPTION OF STATISTICAL METHODS

10.4.1 GENERAL APPROACH

By cross-over design, each participant will act as his or her own control, permitting between and within group comparisons. Analyses will be performed on an intention-to-treat and modified intention-to-treat basis, separately. Comparisons of values between HD treatments will be performed by repeated-measures analysis of variance (ANOVA; or non-parametric methods depending on data type) for continuous outcomes and generalized estimating equations for categorical outcomes. Analogous analyses will be performed in both the intention-to-treat and modified intention-to-treat datasets. All statistical estimates will be tabulated along with their corresponding 95% confidence intervals. All reported P values will be 2-sided; <0.05 representing significance. All hypothesis tests that are observed to be statistically non-significant will be interpreted as such and reported as being inconclusive. However, as this is a small, pilot study, the magnitude of estimates and the corresponding confidence intervals will be considered in the results interpretation.

10.4.2 ANALYSIS OF THE PRIMARY EFFICACY ENDPOINT(S)

Comparisons of values for the binary primary endpoints of hypotension and troponin T rise $\geq 10\%$ between HD treatments will be performed using generalized estimating equations. Comparisons of values for the continuous

primary endpoint of global longitudinal strain change will be performed using ANOVA or non-parametric methods depending on data type.

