4.2.1 PRIMARY ENDPOINT

- 1) Intradialytic hypotension: measured on a per-treatment basis; defined as nadir systolic BP <90 mmHg
- 2) Troponin T change: measured at the 7th treatment of each phase; defined as pre-HD – post-HD troponin T (ng/mL) and percentage change (troponin T rise) $\geq 10\%$
- 3) Left ventricular global longitudinal strain (GLS) on TTE: measured at baseline and 30 minutes before HD end during 7th treatment in the first phase of each treatment type (once during conventional and once during UF profiled treatment); defined as % GLS change (intradialytic GLS – baseline GLS), see Appendix A for TTE protocol. A change $\geq 2.5\%$ indicates a clinically important change in GLS.

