10.5 SAMPLE SIZE

This cross-over study is designed as a pilot study to test for efficacy signals. However, with its cross-over design in which each participant acts as his or her own control, we are powered to detect clinically and statistically significant differences across arms within patients. With a sample size of 30, we have 80% power to detect a 5.9 mmHg difference in nadir SBP (S.D. 8), a ≥ 0.07 ng/mL troponin T difference (S.D. 0.1), a 2.2% strain difference (S.D. 3), and 4% ejection fraction difference (S.D. 5); all clinically meaningful differences. We have 80% power to detect a 31% absolute difference in the binary endpoint of Troponin T change >0.1 ng/mL (event rate=20%).

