Depending on the type of various endpoints, we propose to perform the following tests to test the difference between UF profile and conventional treatment.

- **Binary Outcomes**
 - We will perform repeated measure logistic regression by regressing the binary outcome on the treatment indicator and test if the coefficient before the treatment indicator is significant. Each subject will have a random intercept. The model is given by
$$\text{logit}(\text{outcome}) \sim 1 + \text{treatment} + (1|ID)$$
- **Continuous Outcomes**
 - We will perform repeated measure linear regression by regressing the continuous outcome (percentage outcome will be log-transformed) on the treatment indicator and test if the coefficient before the treatment indicator is significant. Each subject will have a random intercept. The model is given by
$$\text{outcome} \sim 1 + \text{treatment} + (1|ID)$$
- **Categorical Outcomes**
 - We will perform repeated measure multinomial regression by regressing the categorical outcome on the treatment indicator and test if the coefficient before the treatment indicator is significant. Each subject will have a random intercept. The model is given by
$$\text{multi-logit}(\text{outcome}) \sim 1 + \text{treatment} + (1|ID)$$

Quality Check

For patients who dropped out during the study, normalize endpoints to the same scale as the other patients, depending on the type of endpoints.

Sensitivity Analyses

1. Exclude participants who dropped out from all analyses.
2. Exclude participants who had endpoint data drawn "off-schedule" (troponin T, symptoms, etc.) from individual endpoint analyses.
3. Exclude participants who had an abnormality with their troponin T blood draw from troponin T-related analyses.
4. Test for difference by order of randomization (UF profiling --> conventional --> UF profiling --> conventional) vs. (conventional --> UF profiling --> conventional --> UF profiling)
5. Test for difference by clinic (site 1 vs. site 2)

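### Troponin T is a primary endpoint in two forms, but only the 10% rise has a named primary test, and no power is given for that form

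*Combined protocol and SAP*

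**What the plan says.** Protocol 4.2.1 gives the second primary endpoint two forms in one sentence: "defined as pre-HD – post-HD troponin T (ng/mL) and percentage change (troponin T rise", the latter with a threshold of at least 10%. Section 7.2.1 schedules pre- and post-dialysis samples at the seventh treatment of every phase, so each participant yields two changes per condition.

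Section 10.4.2, which assigns methods to the primary endpoints, takes troponin T only in its binary form: "Comparisons of values for the binary primary endpoints of hypotension and troponin T rise" of at least 10% go to generalized estimating equations. The one continuous primary endpoint it names is strain: "primary endpoint of global longitudinal strain change will be performed using ANOVA or non-parametric methods depending on data type". The continuous troponin change is not named among the secondary analyses (10.4.3) or the exploratory analyses (10.4.11) either.

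Two general statements apply to continuous outcomes without naming endpoints. Section 10.4.1 provides "repeated-measures analysis of variance (ANOVA; or non-parametric methods depending on data type) for continuous outcomes". The SAP, under Primary Analysis, says "We will perform repeated measure linear regression by regressing the continuous outcome (percentage outcome will be log-transformed) on the treatment indicator", with a random intercept per participant.

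Section 10.5 states 80% power with 30 participants for a 0.07 "ng/mL troponin T difference (S.D. 0.1"), and then for a 31-point absolute difference in a binary troponin endpoint cut at 0.1 ng/mL with an event rate of 20%. It gives no figure for the rise of at least 10%. Section 10.4.9 counts three primary outcomes and plans analyses with and without a Bonferroni correction.

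**The concern.** Three troponin definitions are in play: the ng/mL change, the rise of at least 10%, and the change above 0.1 ng/mL. The only one with a named primary test is the only one without a power statement.

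Two things are at stake. The first is interpretation. If the continuous change favours UF profiling and the 10% rise does not, or the reverse, the plan does not say which result answers the primary question. If both are tested as primary, there are four primary tests (hypotension, troponin change, troponin rise, strain), and a three-way Bonferroni correction no longer matches. The second is precision. If the 10% rise carries the primary claim, a trial of 30 completers relies on a yes/no reduction of a measurement that it already collects on a continuous scale.

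**Working it through.** **1. Inputs.** From 10.5: n = 30, power 80%, difference 0.07 ng/mL, SD 0.1 (0.07/0.1 = 0.7 SD). From 10.4.1: "All reported P values will be 2-sided; <0.05 representing significance". Not in the documents: the event rate for a rise of at least 10%, and the within-participant correlation. Both are assumed below and varied.

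**2. Reproducing 10.5 for the continuous change.** Treating the conditions as two independent samples of 30, the detectable difference is (1.960 + 0.842) × 0.1 × √(2/30) = 0.0723 ng/mL (0.0736 with the t distribution). This rounds to the stated 0.07, so that is 10.5's basis. A paired calculation taking 0.1 as the SD of differences would give 0.053. At exactly 0.07, power is Φ(0.07/[0.1 × √(2/30)] − 1.960) = Φ(2.711 − 1.960) = 77.4%, and 80% power needs 33 per condition.

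**3. Information kept by a cut.** For a normal variable cut at event rate p, with independent observations and z_p the corresponding normal quantile, the share kept is φ(z_p)²/[p(1−p)]. For example, at p = 0.20 it is 0.280²/0.16 = 0.490.

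**4. Power after the cut.** Cut the same normal variable at control rate p1 and reduce it by 0.7 SD, giving p2. With p̄ the mean of p1 and p2, and n = 30 per condition, power = Φ{[(p1 − p2) − 1.960√(2p̄(1−p̄)/n)] / √([p1(1−p1) + p2(1−p2)]/n)}. For 20% versus 6.2% this is Φ{[0.138 − 0.171]/0.085}, about 35%.

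| Control event rate (assumed) | Information kept | Information lost | Rate after 0.7 SD reduction | Power, 30 per condition | n per condition for 80% |
|---|---|---|---|---|---|
| 50% | 63.7% | 36.3% | 24.2% | 54% | 54 |
| 30% | 57.6% | 42.4% | 11.0% | 44% | 71 |
| 20% | 49.0% | 51.0% | 6.2% | 35% | 92 |
| 10% | 34.2% | 65.8% | 2.4% | 23% | 156 |
| Not cut | 100% | 0% | – | 77% | 33 |

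The information column describes small effects. At a 0.7 SD reduction the sample-size ratios are 33/54 = 0.61 and 33/92 = 0.36.

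**5. Sensitivity to correlation.** For within-participant comparisons, the share kept is multiplied by (1 − ρ)/(1 − ρ_b), where ρ_b is the correlation of the dichotomised values. At an assumed ρ of 0.5 the loss is 52% (50% event rate), 65% (20%) and 77% (10%). Over event rates of 10% to 50% and ρ from 0 to 0.7, it runs from 36% to 83%.

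**6. The binary figure in 10.5.** It uses a different cut-off, so it does not describe the 10% rise. Read as 20% versus 51% with 30 per condition, two-sided power is 71.9%, not 80%; one-sided it is 82.0%. If 20% is the control rate, a 31-point fall, which is the direction hypothesised in 10.2, cannot occur.

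**The case against.** A reader might infer that the continuous troponin data will be thrown away. The documents do not support that. The ng/mL change is a defined primary endpoint, and both 10.4.1 and the SAP's primary-analysis section give a method for continuous outcomes that could cover it. This stands: the defect is an undesignated primary analysis, not proof of discarded data.

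A reader might also infer that about half the information is lost, as if 15 of 30 participants were analysed. That needs a 20% event rate, which 10.5 attaches to the 0.1 ng/mL cut-off and not to the 10% rise. The calculation further assumes normality, independent observations and a cut on the same scale, whereas the 10% rise is relative and 10.5's difference is absolute. This stands too, so only an assumed range can be given.

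Nor does 10.5 rest on the continuous form alone, since it also powers a binary troponin endpoint. And if only the 10% rise is tested, there are exactly three primary tests, as 10.4.9 counts. The fourth appears only if both forms are tested.

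Finally, the 10% threshold is prespecified, and 10.4.1 says that this small pilot will weigh estimates and confidence intervals. Keeping a responder definition as primary would be defensible. It would still have to be designated and powered, which the plan does not do.

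**Conclusion.** The point holds as a mismatch between 4.2.1, 10.4.2 and 10.5. Troponin T is primary in two forms, only the 10% rise is given a named test, and 10.5 powers the other form and a third one. The general continuous-outcome models do not settle which result is primary.

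That much rests on the text alone. The size of the loss rests on the assumptions set out in the objection: about 36% to 66% of the information for event rates of 50% down to 10%, more if values within a participant are correlated. The fall in power from about 77% to about 54% or 35% is on 10.5's two-sample basis. It compares the two forms and does not forecast the power of the crossover analysis with two values per condition. The point should be resolved before analysis; it does not invalidate the trial.

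**What to change.** In 4.2.1, 10.4.2 and the SAP, name the continuous troponin T change as the single primary troponin analysis: one value per phase, in a mixed model with treatment, period and a participant random intercept. Use either the ng/mL scale that 10.5 already powers, or the log of the post/pre ratio with 10.5 restated for that scale, because the 0.07 and 0.1 ng/mL figures do not carry over to it. Label the rise of at least 10% supportive. Remove the 0.1 ng/mL power statement from 10.5 or align it with the supportive definition. The count of three primary tests in 10.4.9 then stands.

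No new data are needed, since 7.2.1 already provides the samples. The cost is wording in a few protocol sections and the SAP, a revised power statement if the log scale is chosen, and a cut-off result that becomes supportive.
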